10.7. Safety

10.7.1. Adverse Events

Adverse Events (AEs) will be summarized. To select events for summarization when there are multiple occurrences of an event for a subject, AEs will be sorted by severity and relationship to study drug (i.e., severity will be sorted as mild, moderate, and severe; relationship will be sorted as not related and related).

Adverse Events (AEs) will be coded according to MedDRA version 23.0 Update. All data will be listed and summarized in the safety population.

Treatment emergent AEs (TEAEs) will be defined as AEs that first occurred or worsened on or after the date of first dose of study drug. Treatment emergent SAEs (TESAEs) will be defined as SAEs that first occurred or worsened on or after the date of first dose of study drug.

Adverse event (AE) summaries will be provided for the number of subjects experiencing at least one event overall and in each treatment group. This will be provided for all AEs, TEAEs, SAEs and TESAEs. All will be presented overall and divided into ocular and non-ocular AEs where ocular events are defined as those where an eye is indicated in the eCRF form. Percentages for the subject based summaries will be calculated based on the number of subjects in the safety population.

Incidence of Adverse Events (AEs): The per subject incidence of TEAEs for each system organ class (SOC) and preferred term (PT) will be summarized. If a subject reports the same PT multiple times, then that subject will only be counted once for that PT. As with the PT, if a subject reports multiple TEAEs within the same system organ class, then the subject will only be counted once for that system organ class. Summaries will be further divided by ocular and non-ocular.

Relationship of Adverse Events (AEs) to the Study Drug: An overall summary of AEs by relationship to the study drug will be presented separately for each treatment group. The relationships indicate the possibility that the study drug caused the event. The possible grades of relationships are “Not Related” and “Related”. If a subject reports multiple occurrences of the same AE, only the most strongly related occurrence would be presented for all subject level summaries. The per subject incidence of TEAEs related to study drug for each SOC, and PT for AEs related to study drug will be summarized.

Severity of Adverse Events (AEs): An overall summary of AEs by severity will be presented separately for each treatment group. If a subject reports multiple occurrences of the same AE, only the most severe event will be presented for all subject level summaries. The order of severity will be “Mild,” “Moderate,” and “Severe”. The per subject incidence of severe TEAEs for each SOC, and PT will be summarized. Percentages will be calculated based on the number of subjects in the safety population.

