4.2. Exclusion Criteria

The following are exclusion criteria for prospective study subjects to be confirmed from Day -14 – Day -2 (at Visit 1) prior to randomization:

1. Subject has any intraocular inflammation (cells and flare in the anterior chamber) or ocular pain (pain score of >0) in either eye prior to surgery.
2. Subject has any extraocular inflammation in the study eye prior to surgery (blepharitis is allowed if only scurf is present without any concurrent conjunctivitis or lid erythema/edema) or ongoing uveitis.
3. Subject has a history of diabetic retinopathy and/or previous vitrectomy in the study eye within the last 2 years prior to Screening which, in the investigator's opinion, is clinically significant and could impact the normal outcome of an uncomplicated cataract surgery.
4. Subject has a diagnosis of severe dry eye in the study eye.
5. Subject has any sign of iritis or scleritis in the study eye.
6. Subject has a history of glaucoma surgery in the study eye within the last 2 years prior to Screening.
7. Subject has a history of retinal surgery in the study eye within the last 2 years or plans to undergo retinal surgery in the study eye during the study period (from Screening through Day 32)

8. Subject has a history of Fuchs' dystrophy in the study eye.
9. Subject has guttata or chalazion in the study eye.
10. Subject has undergone radial keratotomy, photorefractive keratotomy, advanced surface ablation, corneal transplant, or LASIK in the study eye within the last 2 years prior to Screening.
11. Subject plans to undergo cataract surgery in the non-study (fellow) eye during the study period (from Screening through Day 32).
12. Subject plans to undergo additional ocular surgery (including femtosecond laser-assisted cataract surgery, minimally invasive glaucoma surgery, astigmatic keratotomy, limbal relaxing incision surgery, mechanical pupillary expanders, conjunctival incisions, and vitrectomy) in either eye during the study period (from Screening through Day 32).
13. Subject has a history of intraocular injections in the study eye within 6 months prior to Screening.
14. Subject has a history of herpes simplex infection in either eye.

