5. STUDY DRUG/INSTRUCTIONS FOR USE AND ADMINISTRATION

The study drug will be masked, packaged and labeled in a manner consistent with the study design. The Sponsor or designee shall provide the packaging of the study drug and the labeling of subject numbers according to a validated SAS® computer-generated randomization list. The study drug will be identified as a new drug, limited by Federal law to investigational use, manufactured and packaged for Surface Pharmaceuticals.

Subjects will be randomly assigned to receive masked study drug (either 0.2% BSP ophthalmic solution or vehicle) for 16 days BID. Subjects will receive instructions for dosing at home and for completing a dosing and pain assessment diary during the study dosing phase (Day -1 to Day 14).

During the 16-day dosing period, a total of 32 doses (2 doses each day, once in the morning and once in the evening, preferably 8-12 hours apart) will be instilled in the study eye by the subject (or their caregiver).

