8. CLINICAL ASSESSMENTS/EXAMINATION PROCEDURES

The ophthalmic examinations listed below will be conducted in the surgery eye (study eye) and in the order specified. The fellow eye (non-study eye) may be examined at the investigators' discretion.

Subject Assessment of Pain via Diary: Surgery eye (study eye) pain will be evaluated prior to each study drug dose using a pain scale included in the dosing and pain assessment diary that subjects complete at home.

Investigator Assessments include the following:

Visual Analog Scale (VAS) (ocular symptoms): Eye pain/discomfort will be evaluated at Screening Visit 1 (Day -14 to Day -2) and at Visit 3 through Visit 7 (Day 1 through Day 32) using a VAS, scoring from 0 to 100 using a mark on a 100 mm line (0 = absent; 100 = maximum).

Best-Corrected Visual Acuity (BCVA): BCVA will be measured at Screening Visit 1 (Day -14 to Day-2) and at Visit 3 through Visit 7 (Day 1 through Day 32) (log of the minimum angle of resolution [logMAR] score using ETDRS [Early Treatment Diabetic Retinopathy Study] chart will be used to measure BCVA). A pinhole test may be performed at Visit 3 (Day 1).

Biomicroscopy: Slit lamp biomicroscopy, including the evaluation of anterior chamber cell (ACC) and anterior chamber flare, chemosis, bulbar conjunctival injection, ciliary injection, corneal edema, and keratic precipitates will be conducted by a board-certified ophthalmologist at Screening Visit 1 (Day -14 to Day -2) and at Visit 3 through Visit 7 (Day 1 through Day 32).

Ophthalmoscopy: Ophthalmoscopy will be performed at Screening Visit 1 (Day -14 to Day-2) and Visit 5 (Day 15) by a board-certified ophthalmologist. Ophthalmoscopy will be performed at Visit 7/Early Discontinuation Visit only if not performed at Visit 5.

Intraocular Pressure (IOP): IOP will be measured at Screening Visit 1 (Day -14 to Day-2) and at Visit 3 through Visit 7 (Day 1 through Day 32) in mmHg using a Goldmann applanation tonometer.

Standard examinations for subjects undergoing cataract surgery will be conducted by the investigator or qualified designated staff. However, ophthalmoscopy and biomicroscopy examinations will be performed by the same board-certified ophthalmologist who performs a subject's cataract surgery. All ratings and procedures should be performed by the same examiner from visit to visit whenever possible.

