9. ADVERSE EVENTS

Throughout the course of the study, the investigator must remain alert to possible adverse events or untoward findings. If adverse events occur, the first concern will be the safety of the subject. Appropriate medical intervention will be provided by the investigator.

Adverse Event (AE) Definition: An AE is any untoward medical occurrence associated with the use of a study drug in a clinical investigation subject, whether or not considered related to the study drug.

Adverse Event Reporting Period: The AE reporting period for this trial begins upon signing the ICF and ends at the completion of the subjects' final study visit exam. All AEs reported by the subject during the course of the study, or elicited by questions from the investigator, or noted as a result of procedures carried out on the subject, during the AE-reporting period must be recorded by site staff in the source documents and on the AE eCRF, whether or not the event is considered related to the study drug. In addition, any known untoward event that occurs subsequent to the AE reporting period that the investigator assesses as related to the study drug should also be reported as an AE.

Serious Adverse Event (SAE) Definition: A serious adverse event (SAE) or reaction is any untoward medical occurrence that at any dose:

- Results in death
- Is immediately life-threatening or immediately sight-threatening in the study eye (surgery eye)
- Requires inpatient hospitalization or prolongation of existing hospitalization
- Results in persistent or significant incapacity or substantial disruption of the ability to conduct normal life functions
- Is a congenital anomaly/birth defect
- Is an important medical event that may jeopardize the subject or may require medical intervention to prevent one of the outcomes listed above

SAE Reporting: SAEs must be immediately reported (within 24 hours of awareness of the event) to designated CRO and will be clearly documented in the source documents and on the appropriate AE eCRF and SAE Report Form. The investigator must also notify the IRB of any SAEs, according to the IRB's guidelines.

Pre-existing Conditions: In this trial, a pre-existing condition (i.e., a disorder present before the AE-reporting period started and noted on the Systemic and/or Ocular Medical History Forms) should not be reported as an AE unless the condition worsens or episodes increase in frequency or severity during the AE-reporting period.

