BCVA: A worsening of 3 lines or more in log of the minimum angle of resolution (logMAR) score in the study eye from baseline or any prior visit should be captured in the source documents and on the appropriate case report form as an AE.

IOP: An increase from baseline or any prior study visit of 10 millimeters of mercury (mmHg) in IOP in the study eye should be captured in the source documents and on the appropriate eCRF as an AE. An IOP of 30 mmHg or higher will be reported as an SAE.

Biomicroscopy: Anterior chamber cell and flare, chemosis, bulbar conjunctival injection, ciliary injection, corneal edema, and keratic precipitates will be assessed in the study. Since the severity of these assessments will be recorded and carefully monitored during the study, worsenings do not need to be recorded as AEs unless the investigator judges it appropriate. Any treatment-emergent findings (i.e., findings that were not present prior to treatment or a worsening relative to the pretreatment baseline) outside of these assessments should be recorded as an AE.

Ophthalmoscopy: A new finding or a significant worsening (2 units or more) from baseline should be recorded as an AE.

VAS: Pain/discomfort will be assessed in the study eye. Since the severity of these assessments will be recorded and carefully monitored during the study, worsenings do not need to be recorded as AEs unless the investigator judges it appropriate.

AE Considerations: Additional exams may be scheduled as necessary to ensure the safety of the subjects during the study period. Subjects discontinued due to an AE should be seen for post-study follow-up visits, as needed. Adverse events considered related to study drug that have not resolved or stabilized by the final study visit will be followed during post-study follow-up visits at the discretion of the investigator until the incident has resolved or stabilized and will be documented in the source documents and AE eCRF. Where appropriate, additional written reports and documentation will be provided. Adverse events considered not related to study drug that have not resolved or stabilized by the final study visit will be noted as ongoing in the eCRF, followed at the discretion of the investigator, and recorded in the source documents.

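### Ocular adverse event tables do not separate the dosed, operated study eye from the fellow eye (minor)

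*Combined protocol and SAP*

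**What the plan says.** Section 10.7.1 sets the classification: "ocular events are defined as those where an eye is indicated in the eCRF form". The subject-level summaries of AEs, TEAEs, SAEs and TESAEs are given overall and then as ocular and non-ocular. For the SOC and preferred-term incidence tables, "Summaries will be further divided by ocular and non-ocular". No AE table anywhere in the plan separates the two eyes.

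The same section counts a subject once per preferred term and once per SOC. Its severity paragraph shows only the most severe of repeated occurrences of the same AE. Neither rule mentions the eye. The paragraphs on related and severe TEAEs state no ocular split at all.

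Elsewhere the two eyes are treated differently:

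- Section 5 directs all 32 doses to the study eye, and Section 4 describes unilateral surgery.
- Section 4.2 lists as an exclusion: "Subject plans to undergo cataract surgery in the non-study (fellow) eye during the study period".
- Section 8 schedules the ophthalmic examinations in the study eye and adds: "The fellow eye (non-study eye) may be examined at the investigators' discretion".
- Section 9 requires recording of "All AEs reported by the subject during the course of the study, or elicited by questions from the investigator", with no restriction to one eye.
- Section 9 ties its measurement-based AE rules to the study eye. A 10 mmHg rise "in IOP in the study eye should be captured in the source documents and on the appropriate eCRF as an AE", and the BCVA rule concerns a worsening of the logMAR "score in the study eye from baseline or any prior visit should be captured". The sight-threatening SAE criterion is also limited to that eye.

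**The concern.** Ocular safety is the first item in the study objective (Section 1). The fellow eye receives neither drug nor planned surgery, so its events say little about local drug effect, yet they count fully in the ocular tables. If they arise at similar rates in both arms, as one would expect in an undosed eye under randomization, they add the same background to each arm and pull the arms together.

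The counting rules add a second problem. A subject with a mild study-eye event and a severe fellow-eye event under the same preferred term appears once, as severe. The table alone cannot show that the severe event was in the undosed eye.

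**Working it through.** The documents give no AE rate and no safety power, so there is no stated figure to reproduce. The calculation below is an illustration, and every rate in it is an assumption.

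**Inputs.** From the documents: 40 subjects per arm (Section 2), subject-level incidence, and the safety population as denominator (Section 10.7.1). Assumed: p, the study-eye ocular TEAE rate, at 25% v 10% or 15% v 5%; and f, the fellow-eye rate, equal in both arms and independent of study-eye events.

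**Formulas.** A subject counts as ocular if either eye has an event:

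pooled rate = 1 - (1-p)(1-f)

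Subtracting the vehicle rate from the active rate gives

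pooled risk difference = (1-f) × (p_active - p_vehicle)

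**Example at f=5%, 25% v 10%.** Active: 1 - 0.75×0.95 = 28.75%. Vehicle: 1 - 0.90×0.95 = 14.50%. The difference is 14.25 points (0.95×15) and the ratio is 28.75/14.50 = 1.98.

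| Study-eye rates | f | Pooled rates | Risk difference (points) | Risk ratio |
|---|---|---|---|---|
| 25% v 10% | 0 | 25.00% v 10.00% | 15.00 | 2.50 |
| | 1% | 25.75% v 10.90% | 14.85 | 2.36 |
| | 2% | 26.50% v 11.80% | 14.70 | 2.25 |
| | 5% | 28.75% v 14.50% | 14.25 | 1.98 |
| | 10% | 32.50% v 19.00% | 13.50 | 1.71 |
| 15% v 5% | 0 | 15.00% v 5.00% | 10.00 | 3.00 |
| | 1% | 15.85% v 5.95% | 9.90 | 2.66 |
| | 5% | 19.25% v 9.75% | 9.50 | 1.97 |
| | 10% | 23.50% v 14.50% | 9.00 | 1.62 |

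**In subjects.** The expected number per arm with a fellow-eye event is 40×f: 0.4 at 1%, 0.8 at 2%, 2 at 5% and 4 at 10%.

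The risk difference barely moves at low f. The risk ratio is more sensitive, because the added background is large relative to a small vehicle rate. At f=0 nothing changes.

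**The case against.** A reader might infer that the pooling hides a drug effect, or that it costs the trial power to detect one. The documents do not support either.

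- **No fellow-eye rate is given, and several features hold it down.** Scheduled examinations are in the study eye, the BCVA and IOP triggers apply to that eye, planned surgery in either eye beyond the study procedure is excluded, and pre-existing conditions count only if they worsen. Against this, some exclusions cover the study eye alone (severe dry eye; active corneal or conjunctival pathology). A fellow eye with such a condition can enter the trial, and its worsening would be an AE. A low rate is plausible but not assured.
- **No test is planned.** Section 10.7.1 specifies counts, percentages and incidences, so a power figure would describe an analysis that nobody intends to run.
- **The risk difference is robust.** Even at f=10% it falls only from 15.0 to 13.5 points under the 25% v 10% assumption.
- **Other safety data are unaffected.** BCVA, IOP, biomicroscopy and ophthalmoscopy are scheduled in the study eye. The related-TEAE table should screen out some fellow-eye events, though it depends on causality judgment. Section 10.5 lists all collected data, so the affected eye can be traced if the eCRF records which eye it is, but a listing is not a comparative summary.
- **Preferred-term rows should carry less background.** The fellow-eye rate for one term cannot exceed the any-ocular rate, which limits the loss in risk difference. It does not settle the risk ratio, since the vehicle rate for a single term is lower too.

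A reader might also infer that discretionary fellow-eye examination makes pick-up uneven across sites and so biases the comparison. Uneven pick-up is not shown, and under masked randomization site variation does not by itself imply imbalance between arms.

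These points limit the size of the effect. They do not answer the classification rule, or counting rules that let one eye's event stand in for the other's.

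**Conclusion.** The point holds as a minor one. As written, any recorded fellow-eye event is counted with study-eye events in the ocular AE, TEAE, SAE, TESAE and SOC/PT summaries, and the once-per-term and most-severe rules disregard the eye. The likely direction is attenuation of the between-arm contrast, provided that fellow-eye events occur at similar rates in both arms; the exact (1-f) factor also needs independence from study-eye events. Under the assumed 25% v 10%, the effect runs from slight (risk ratio 2.36 at f=1%) to visible (1.71 at f=10%). Which end applies cannot be read from the documents, so material dilution is possible and not demonstrated. The related and severe TEAE tables should not be described as pooled ocular tables, because no ocular split is stated for them.

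**What to change.** In Section 10.7.1:

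- Divide the ocular AE, TEAE, SAE, TESAE and SOC/PT summaries into study eye and non-study eye, using the eye indication on the eCRF.
- Apply the once-per-subject and most-severe rules within each eye.
- Count a bilateral event once in each eye, with a footnote that the two counts need not add to the pooled one.
- Present the study-eye tables as the main ocular AE summary, keeping the pooled table if wanted.

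The cost is a short addition to the text and a few extra tables. No new data are needed, provided that the eCRF field records which eye is affected; the eCRF is not among the documents, so this should be confirmed. Making the change before unmasking avoids a later choice about which ocular table to lead with.
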